6.3 Sample size and power

Based on our preliminary data and prior studies,^{37, 38} the anticipated AKI event rate in the placebo group is **50%**. We hypothesize the AKI event rate in the DFO group will be **34%**, an effect size that has been proposed to be reasonable for studies in AKI.^{86, 87} A total of 296 patients ($n=148$ per group) will provide 80% power to detect the above treatment effect, with a two-sided α of 0.05. Enrollment of 330 patients provides a small buffer for potential early withdrawal from the study, which we anticipate will be uncommon due to the nature of the study (inpatient and short duration).

6.4 Secondary endpoints

Other renal endpoints (clinical)

- Effect of DFO across all stages of AKI, defined by changes in SCr according to the KDIGO criteria⁸⁵ within 7 days of cardiac surgery.
- Requirement for loop or thiazide diuretics in the setting of ≥ 2 hours of oliguria (urine output <0.5 ml/kg/h for ≥ 2 consecutive hours) within 48h of cardiac surgery.
- Incidence of Major Adverse Kidney Events,⁸⁸ defined as any of the following within 7 days following cardiac surgery: $\geq 100\%$ increase in SCr, receipt of RRT, or death.

Other renal endpoints (urinary tubular injury markers)

We will assess the effect of DFO on renal tubular injury using longitudinal measures of urine NGAL and KIM-1, each assessed pre- and postoperatively (**Figure 4**). These injury markers provide complementary data to functional markers (e.g., SCr),⁸⁹ and have been used in multiple RCTs.⁹⁰⁻⁹³ Urine NGAL and KIM-1 will be normalized to the urine creatinine to account for the influence of dilution.

Extrarenal acute organ injury

We will assess the incidence of postoperative myocardial injury, atrial fibrillation, prolonged mechanical ventilation, and sepsis. The consensus definition and anticipated incidence for each endpoint is described in **Table 5**, and each was chosen based on a strong biologic rationale (**Table 5**). Assessment of atrial fibrillation will be limited to patients who do not have it at baseline. For sepsis, we will document the suspected or confirmed source of infection: pneumonia, genitourinary, biliary, bacteremia, sternal wound infection, or other. We will also document the presence/absence of septic shock, defined as sepsis with persistent hypotension requiring vasopressors to maintain mean arterial pressure ≥ 65 mm Hg and having a serum lactate level >2 mmol/L despite adequate volume resuscitation.⁹⁴

Table 5. Secondary extrarenal endpoints

Endpoint	Definition	Incidence*	Biologic Rationale
Myocardial injury	Peak postop troponin I [†] elevation >10 times the 99 th percentile URL, assessed on POD1 and 2. ⁹⁵	15%	DFO attenuates cardiac IRI ^{67, 68} and improves myocardial contractility in animals. ⁹⁶ In a RCT in 45 adults undergoing cardiac surgery, patients treated with DFO had a higher LVEF postop compared to placebo. ⁸⁰
AF	[‡] Confirmed on a 12-lead ECG or a rhythm strip, confirmed by a healthcare provider, or treated (either medically [e.g., amiodarone] or with electrical cardioversion). Patients with AF at baseline will be excluded.	40%	In animal models, DFO prevents CPB-associated arrhythmias. ⁶⁹ In patients with chronic iron overload from beta-thalassemia major, arrhythmias are an indication for DFO treatment intensification. ⁹⁷
Prolonged ventilation	[‡] Requirement for mechanical ventilation >24h postop.	20%	In animal models, DFO attenuates the severity of mechanical ventilation- and lipopolysaccharide-induced acute lung injury. ^{70, 71}
Sepsis	[‡] Life-threatening organ dysfunction caused by a dysregulated host response to infection (assessed within 7d postop). Organ dysfunction is defined as an acute increase in the total SOFA score ≥ 2 points consequent to the infection.	10%	DFO improves monocyte phagolysosome function in vitro. ⁹⁸ Moreover, DFO improves survival in animal models of sepsis. ^{75, 76, 99}

*Anticipated incidence based on our preliminary data and published literature. [†]Troponin I is less affected by skeletal muscle breakdown than troponin T.¹⁰⁰ [‡]Defined as per the Third International Consensus Definition (Sepsis-3).⁹⁴ Abbreviations: AF, atrial fibrillation/flutter; DFO, deferoxamine; ICH, intracerebral hemorrhage; LVEF, left ventricular ejection fraction; POD, postoperative day; URL, upper reference limit.

We will assess time to liberation from IV vasoactive medications, as well as the Vasoactive-Inotropic Score during the first 24 hours. Finally, we will assess the number of ventilator-, hospital-, and ICU-free days to day 28, as well as all-cause hospital mortality. Patients who die prior to 28 days will be assigned 0 ventilator-, hospital-, and ICU-free days.

Iron and oxidative stress markers

We will assess the effect of DFO on iron and oxidative stress markers, including catalytic iron, total iron, total iron binding capacity, ferritin, hepcidin, F(2)-isoprostane, and myeloperoxidase, each assessed pre- and postoperatively (**Figure 4**).

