Primary Objectives and Primary Endpoint	
Primary objective: To evaluate the potential efficacy of deferoxamine in reducing the risk of postoperative AKI in patients undergoing cardiac surgery.
 
Primary endpoint: Incidence of postoperative AKI, defined as follows: urine output <0.5 ml/kg/h for 6 consecutive hours (assessed within the first 48h or until the Foley catheter is removed, whichever occurs first); an increase in serum creatinine ≥0.3 mg/dl within the first 48h; an increase in serum creatinine ≥50% in the first 7 days; or receipt of renal replacement therapy in the first 7 days.

Secondary Objectives and Corresponding Endpoints	
Secondary objectives:
 
 ▪ To evaluate the potential efficacy of deferoxamine in reducing renal tubular injury in patients undergoing cardiac surgery. ▪ To evaluate the potential efficacy of deferoxamine in reducing the risk of postoperative myocardial injury, atrial fibrillation, prolonged mechanical ventilation, and sepsis in patients undergoing cardiac surgery. 
Secondary endpoints:
 
 ▪ Urinary markers of tubular injury, NGAL and KIM-1, assessed preoperatively, at the end of CPB, on arrival to the ICU, and daily for 2 days postoperatively. ▪ Postoperative myocardial injury, atrial fibrillation, prolonged mechanical ventilation, and sepsis within 7 days following cardiac surgery.
Exploratory Objectives and Corresponding Endpoints	
Exploratory objectives: To test the effects of deferoxamine on circulating markers of iron, oxidative stress, and inflammation
 
Exploratory endpoints: Circulating markers of iron status (catalytic iron, total iron, total iron binding capacity, ferritin, and hepcidin), oxidative stress (F[2]-isoprostane and myeloperoxidase), and inflammation (monocyte phenotype), each assessed pre- and postoperatively.

Sites	Brigham and Women's Hospital (BWH) Massachusetts General Hospital (MGH) Beth Israel Deaconess Medical Center (BIDMC)
Study Duration	Estimated total study duration is 4 years
Data and Safety Monitoring Committee (DSMB)	A DSMB will convene prior to study launch and after enrollment of 10, 25, 50, and 75% of the total enrollment has taken place to review safety data and any unanticipated problems. The DSMB will make recommendations as needed. The DSMB will not perform a futility analysis or consider early study completion for efficacy.

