3.2 Exclusion criteria (at the time of screening)

1. AKI, defined as any of the following:
 - Increase in serum creatinine ≥ 0.3 mg/dl in 48h
 - Increase in serum creatinine $\geq 50\%$ in 7d (if no value available in last 7d, use most recent value in last 3 months)
 - Urine output ≤ 0.5 ml/kg/h \times 6 consecutive hours (only assessed in patients with hourly monitoring via Foley catheter)
 - Receipt of renal replacement therapy (RRT) within 7d
2. Advanced chronic kidney disease (eGFR < 15 ml/min/1.73m² or end-stage kidney disease receiving RRT)
3. Hemoglobin < 8 g/dL (closest value in the prior 3 months)
4. Fever (temperature $\geq 38^{\circ}\text{C}$) in the last 48h
5. Suspected or confirmed bacteremia, endocarditis, or pyelonephritis
6. Pneumonia, aspiration, or bilateral pulmonary infiltrates from an infectious etiology reported on chest x-ray or CT scan in the last 7d
7. Positive COVID-19 test in the last 10d
8. Chronic iron overload (including conditions such as hemochromatosis and beta thalassemia major) or previous iron chelation therapy (including prior participation in DEFEAT-AKI)
9. Known hypersensitivity to DFO
10. Taking prochlorperazine
11. Known severe hearing loss
12. Pregnant or breastfeeding. Women of childbearing potential will not be included without documentation of a negative pregnancy test, unless they have previously undergone hysterectomy or bilateral oophorectomy. Women of child bearing potential will be defined as any woman who has begun menstruation and not yet reached menopause. Menopause will be defined as any woman over the age of 45 who has not had a menstrual period for at least 12 consecutive months.
13. Prisoner
14. Concurrent participation in another interventional research study in which the intervention has potential interaction with DFO
15. Surgery to be performed under conditions of circulatory arrest
16. Receiving extracorporeal membrane oxygenation
17. Durable ventricular assist device (VAD) prior to surgery (does not include Impella device or intra-aortic balloon pump)
18. Any condition which, in the judgement of the investigator, might increase the risk to the patient
19. Conflict with other research studies

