5.4 Biological sample collections

Overview

We will collect blood and urine samples at five time points: preoperatively (after insertion of an arterial line [for blood] and after insertion of a Foley catheter [for urine]); at the end of CPB; on arrival to the ICU; and on postoperative days 1 and 2 (**Figure 4**). Blood will be obtained from arterial or central venous catheters, which are inserted preoperatively as part of routine clinical care. If, during the course of the study, neither an arterial nor central venous catheter remains in place (e.g., on postoperative day

2), blood will be obtained by peripheral venipuncture by a phlebotomist, in which case all efforts will be made to time the blood collection with a clinical blood draw to minimize discomfort. The total volume of blood collected will be 80mL. Blood will be collected in serum and heparinized vacutainers, since EDTA chelates iron. Urine (12cc) will be obtained from Foley catheters or from a clean catch voided sample if the Foley catheter is no longer in place.

Blood volume

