The volume of blood drawn at the other time points will be 10mL, as shown in **Figure 4**. This will include 5mL of blood drawn into a serum vacutainer and 5mL drawn into a heparinized plasma vacutainer. The serum and plasma will be centrifuged, subaliquoted, and stored at -80°C . 5mL of blood contains approximately 2.5mL of plasma/serum (approximately 50% of whole blood is plasma/serum), which will allow us to archive eight 300 μL plasma and serum aliquots at each time point. These aliquots will be used to measure the following parameters, and for storage for future hypotheses and mechanistic pathways: catalytic iron, total iron, total iron binding capacity, ferritin, hepcidin, troponin I, and oxidative stress parameters (F[2]-isoprostane and myeloperoxidase). Finally, we will collect the buffy coat (for DNA isolation) on ICU arrival and on post-operative day (POD) 1 (**Figure 4**).

Patients with a hemoglobin level <8 g/dl are excluded (section 3.2). Additionally, if during the course of the study the patient's clinical team determines that collection of blood is unsafe for the patient (e.g., if the patient is experiencing major bleeding postoperatively) then the blood sample will not be collected until the clinical team determines that it is safe. Urine will be collected for assessment of markers of tubular injury, including NGAL and KIM-1.

Sample processing, cataloging, storing, and monitoring

We will centrifuge samples as soon as possible and no more than 6h after collection and store the plasma, serum, and urine at -80C. At two time points (preoperatively and at the end of CPB) we will also isolate PBMCs and store them in liquid nitrogen. We will use screw cap micro tubes for plasma, serum, and urine samples, each pre-labeled with a unique barcode and a printed label. Each site will catalogue the date and time of collection, processing, and storage at -80C (or in liquid nitrogen, for PBMCs) for each sample. Samples will be transported every 3-6 months from MGH and BIDMC to BWH, which will serve as the central biorepository for the study. The location of each sample will be catalogued using Freezerworks, a sophisticated biorepository management and inventory program.

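### Myocardial injury is judged on postoperative troponin I alone, with no preoperative condition, so any pre-existing injury above the threshold dilutes the estimated effect

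*Combined protocol and SAP*

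**What the plan says.** - **Endpoint.** Section 6.4, Table 5 defines myocardial injury by peak postoperative troponin I above 10 times the 99th "percentile URL, assessed on POD1 and 2", with an anticipated incidence of 15%. The row gives no preoperative ceiling, no required rise from the patient's own value and no exclusion.
- **Neighbouring endpoints.** For atrial fibrillation, section 6.4 says "Assessment of atrial fibrillation will be limited to patients who do not have it at baseline", and the table row repeats "Patients with AF at baseline will be excluded". Section 6.1 judges AKI against the immediate preoperative creatinine. Sepsis in Table 5 needs an acute rise in the SOFA score.
- **Analysis.** Section 6.5 compares binary secondary endpoints by a chi-square test without covariates. Its baseline adjustment is for continuous markers. It also plans a composite of any renal or extrarenal organ injury or hospital death.
- **Population.** Section 3.2 does not exclude recent infarction or raised troponin, and its exclusion of durable assist devices "does not include Impella device or intra-aortic balloon pump". Section 3.4 allows inpatients. Sections 5.2 and 6.2 provide for urgent and emergent surgery.
- **Samples.** Section 5.4 states "We will collect blood and urine samples at five time points: preoperatively" and at four later points. It lists "ferritin, hepcidin, troponin I, and oxidative stress parameters" among the assays on stored aliquots.
- **Window.** The Synopsis gives "Postoperative myocardial injury, atrial fibrillation, prolonged mechanical ventilation, and sepsis within 7 days following cardiac surgery", and section 5.2 also records myocardial injury over 7 days.

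**The concern.** Hypothesis 2 in section 6.5 is about incidence: fewer patients on deferoxamine should develop the injury. A patient who is above the threshold on postoperative days 1 to 2 only because of injury present before surgery has not developed anything that the infusion could have prevented. As the definition stands, that patient is an event in whichever arm they fall. Such events add the same amount to both arms in expectation and pull the risk ratio toward 1.

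The protocol already follows this logic for atrial fibrillation, AKI and sepsis, and the eligibility rules leave room for the problem to arise. What is at stake is the estimate. Section 8.2 says that an effect on AKI or other acute organ injury would lay the groundwork for a phase 3 trial, and a diluted risk ratio would feed that planning. The same events also enter the section 6.5 composite.

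**Working it through.** **1. The plan's own figure.** The only powered comparison is AKI, 50% against 34% (section 6.3). With p̄ = 0.42,

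n per arm = [1.96·√(2·0.42·0.58) + 0.842·√(0.50·0.50 + 0.34·0.66)]² / 0.16² ≈ 148.2, which rounds up to 149.

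The plan states 148, and power at 148 is 79.9%. The figure reproduces, and nothing stated in the plan is numerically wrong. The plan gives no power for myocardial injury.

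**2. Inputs for the illustration.**
- Placebo rate 15% (Table 5).
- 150 per arm: 300 analysable patients (section 6.6), allocated 1:1 (section 4.3).
- Two-sided 5% test (section 6.3).
- *Assumption:* true risk ratio on new injury 0.34/0.50 = 0.68. This is borrowed from the AKI hypothesis; the documents give no effect size for myocardial injury.
- *Assumption:* q, the share of all patients above the threshold on days 1 to 2 from preoperative injury alone. The documents do not give it. I show 0, 2 and 5 percentage points.

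**3. Model.** Patients in the share q are events in both arms, and the drug acts only on the rest. If the 15% includes q:

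- observed deferoxamine rate = q + (0.15 − q)·0.68
- observed risk difference = 0.32·(0.15 − q)
- after restriction: placebo rate (0.15 − q)/(1 − q), risk ratio 0.68, n = 150·(1 − q) per arm
- power = Φ{[|p₁ − p₂|·√n − 1.96·√(2p̄(1 − p̄))] / √(p₁(1 − p₁) + p₂(1 − p₂))}

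For q = 0: p₁ = 0.15, p₂ = 0.102, p̄ = 0.126. The argument is (0.588 − 0.920)/0.468 = −0.709, so power is 24%.

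| q | Observed rates | Observed risk ratio | Risk difference | Power as written | Power after restriction |
|---|---|---|---|---|---|
| 0 | 15.0% vs 10.2% | 0.68 | 4.8 points | 24% | 24% |
| 2 points | 15.0% vs 10.8% | 0.72 | 4.2 points | 19% | 21% |
| 5 points | 15.0% vs 11.8% | 0.79 | 3.2 points | 13% | 17% |

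After restriction, the rates are 13.3% vs 9.0% (147 per arm) at 2 points and 10.5% vs 7.2% (142.5 per arm) at 5 points.

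**4. Alternative reading of the 15%.** If 15% is the rate of new injury only, the placebo rate becomes q + (1 − q)·0.15. At q = 2% the observed rates are 16.7% and 12.0% (risk ratio 0.72, power 21%, or 24% after restriction). At q = 5% they are 19.3% and 14.7% (risk ratio 0.76, power 18%, or 23% after restriction). The direction is the same.

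**5. Sensitivity to the borrowed effect.** With a true risk ratio of 0.50 and the 15% including q, power is 54% at q = 0. At q = 5 points it is 26% as written and 38% after restriction, with an observed risk ratio of 0.67. This is still well short of 80%.

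**The case against.** The strongest reply is that the size is assumed. The share of patients affected is not in the documents, and the 0.68 comes from a different endpoint. Eligibility of urgent cases or balloon-pump patients shows only that some patients may arrive with raised troponin. The model needs patients whose preoperative injury alone exceeds 10 times the URL on days 1 to 2, which is a much higher bar. That stands. A reader might infer that dilution is known to be large, for example with more than half of the 15% already present; nothing in the documents supports this.

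Two other inferences also fail. A reader might take this as a route to a false claim of benefit. Randomization balances pre-existing elevation in expectation, so type I error is unaffected. A reader might also take lost power as the main harm. With the borrowed risk ratio, power is about 24% even with no pre-existing cases, and the restriction recovers only about 2 to 4 points in the table above.

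Part of the remedy may already be intended. Troponin I is listed in section 5.4 beside iron and oxidative stress markers that section 6.4 says are measured before and after surgery. But no text says that the preoperative sample is assayed for troponin I, or gives such a value a role in the endpoint. Table 5 also rests on a cited consensus source that may carry a baseline condition. That cannot be checked here; if it does, the protocol should state it.

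Finally, the difference in windows might be read as a contradiction. The Synopsis can be read as an outer 7-day limit for four endpoints together, with days 1 and 2 inside it. This is mainly a wording point and separate from the baseline issue.

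**Conclusion.** The omission is in the text and its direction is certain: any patient carried over the threshold by preoperative injury moves the estimate toward no effect and also enters the organ-injury composite. The size cannot be set from the documents. On the stated assumptions, a true risk ratio of 0.68 would appear as about 0.72 if 2 of the 15 points pre-exist and as about 0.79 (0.76 if the 15% is new injury only) if 5 do. If no such patients enrol, there is no dilution. The case for change is a cleaner phase 2 estimate of a named secondary endpoint. It is not a claim that the test would become adequately powered or that the trial's error rate is at risk.

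**What to change.** Before unblinding:

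1. State in section 5.4 that troponin I is assayed on the preoperative sample already drawn, which includes 5 mL for serum.
2. In Table 5, restrict the binary endpoint to patients not already above 10 times the 99th percentile URL preoperatively, in parallel with the atrial fibrillation rule. Say whether the composite uses the restricted definition. Keep the present definition as a sensitivity analysis.
3. In section 6.5, add a comparison of log peak troponin I on days 1 to 2, adjusted for log preoperative troponin I. This also covers patients just below the threshold at baseline, who could cross it with little new injury and whom the restriction leaves in.
4. Separately, align the 7-day wording in the Synopsis and section 5.2 with the days in Table 5.

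The cost is one extra assay per patient, if it is not already planned, and a few lines of text. The binary endpoint loses some of its denominator: 3 of 150 per arm at q = 2% and 7.5 of 150 at q = 5%, if preoperative elevation coincides with the carried-over share in the model.

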6.5 Statistical analysis for secondary endpoints

Hypothesis 2: DFO will attenuate peak postoperative increases in urinary markers of tubular injury (NGAL and KIM-1) and iron and oxidative stress, and will reduce the incidence of myocardial injury, atrial fibrillation, prolonged mechanical ventilation, and sepsis. For binary variables we will use the χ^2 test to compare the proportion of patients in each group who develop the endpoint. For continuous variables we will compare baseline (preoperative)-adjusted peak postoperative levels of each marker in DFO- versus placebo-treated patients using the two sample t-test or Wilcoxon rank-sum test depending on the distribution. We will also use a Generalized Estimating Equation for repeated measures to analyze longitudinal assessments of each marker in DFO- versus placebo-treated patients. For analyses of urinary tubular injury markers, we will perform sensitivity analyses using a global rank endpoint to account for anuria as a competing risk.^{101, 102} Finally, we will evaluate a composite endpoint of any renal or extrarenal acute organ injury or hospital mortality.

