1.2.2 Clinical studies

Clinical studies supporting the proposed research include the demonstration of elevated levels of catalytic iron in the circulation of patients at risk of AKI, including both cardiac surgery-associated AKI and AKI in the setting of critical illness.

Catalytic iron and cardiac surgery-associated AKI

We measured plasma catalytic iron pre-, intra-, and postoperatively in 250 adults undergoing cardiac surgery with CPB.²⁷ Catalytic iron levels peaked at the end of CPB, and were higher in patients who developed the composite endpoint of postoperative AKI requiring RRT or death (RRT/death) (Figure 1). In multivariable models, patients with catalytic iron levels in the highest versus lowest quartile on postoperative day 1 had a **3.99-fold higher odds of AKI** (95% CI, 1.60 to 9.93) and a **6.71-fold higher odds of RRT/death** (95% CI, 1.37 to 32.87). Finally, longer duration of CPB ($P<0.001$) and greater number of RBC transfusions ($P<0.01$) each associated with higher catalytic iron postoperatively, consistent with hemolysis as an important source of catalytic iron in this context.²⁷

Catalytic iron and critical illness-associated AKI

We measured plasma catalytic iron levels in 121 patients within 24h of arrival to the intensive care unit (ICU), and found that higher concentrations associated with a greater risk of AKI in both univariate and multivariable models (adjusted odds ratio per 1-SD higher catalytic iron, 1.67; 95% CI, 1.04 to 2.67).⁶⁵ We also measured plasma catalytic iron and other iron parameters in 807 patients with AKI requiring RRT who enrolled in the Acute renal failure Trial Network (ATN) study. Higher quintiles of catalytic iron associated with a monotonic increase in the risk of 60-day mortality (Figure 2A).⁶⁶ Other iron markers were also associated with death, but the magnitude of association was greatest for catalytic iron (Figure 2B).⁶⁶

Conclusions from these data

1. Catalytic iron levels are markedly elevated following CPB.
2. Catalytic iron levels are significantly higher among patients who develop AKI and RRT/death following CPB.
3. Catalytic iron levels rise acutely and early in the course of AKI following CPB surgery, a setting in which the timing of renal injury is known. This establishes CPB surgery as an important setting to test the efficacy of iron chelation in reducing the risk of AKI, as we now propose.

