4.3 Treatment assignment and randomization

Participants will be randomly assigned in a 1:1 fashion to receive DFO or an equal volume of normal saline. Randomization will be stratified by site and by preoperative eGFR (<60 vs. ≥ 60 ml/min/1.73m²) at the time of screening. Treatment assignment lists will be generated centrally by the study biostatistician, [name] PhD, using permuted block sizes of 4 and sent to the research pharmacies at each site. Patients, physicians, nurses, and study investigators will be blinded to treatment assignment.

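### The baseline-adjusted peak marker comparison names two tests that take no covariate and does not say how the adjustment is made; a fixed log-scale ANCOVA would settle it (minor)

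*Combined protocol and SAP*

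**What the plan says.** Section 6.5 gives the continuous-marker analysis in one sentence. The plan is to "compare baseline (preoperative)-adjusted peak postoperative levels of each marker in DFO- versus placebo-treated patients using the two sample t-test or Wilcoxon rank-sum test". The choice is made "using the two sample t-test or Wilcoxon rank-sum test depending on the distribution", with no criterion and no transformation stated. The nearest hint about the adjustment is Hypothesis 2 in the same section: "DFO will attenuate peak postoperative increases in urinary markers of tubular injury". A second analysis follows: "We will also use a Generalized Estimating Equation for repeated measures to analyze longitudinal assessments of each marker". Whether the preoperative value enters that model as a covariate or as an outcome is not stated. A global-rank sensitivity analysis covers anuria.

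On design, section 4.3 states: "Randomization will be stratified by site and by preoperative eGFR", with the eGFR cut at 60. Section 6.5 does not mention these strata.

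On sampling, section 5.4 states: "We will collect blood and urine samples at five time points". These are preoperative, end of CPB, ICU arrival, and postoperative days (POD) 1 and 2.

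The markers concerned are NGAL and KIM-1 (secondary) and the iron and oxidative stress markers, which the synopsis calls exploratory and section 6.4 lists under secondary endpoints.

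**The concern.** A two-sample t-test or a Wilcoxon test compares one response between two groups. Any baseline adjustment must therefore be built into the response beforehand, as a difference, a ratio, a log difference or a regression residual. The plan does not choose among these. Two analysts following the sentence could report different effect measures with different precision, and the test itself is picked after seeing the data.

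At stake are the precision and reproducibility of the marker results. If the adjustment is a change score and the pre/peak correlation is low, the preoperative value can add more noise than it removes. ANCOVA avoids this with data already collected.

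**Working it through.** **The plan's own figure.** The plan gives no SD, effect size or power for any marker, so there is nothing to reproduce for this comparison. The 296 patients in section 6.3 belong to the primary endpoint. The pooled two-proportion formula for 50% against 34% gives 148.2 per arm, rounded up to 149, and power at 148 per arm is 79.9%. The figure reproduces and has no bearing on this point.

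**Inputs.** 300 analyzable patients (section 6.6), so 150 per arm under 1:1 allocation (section 4.3). Assumed, because the documents do not give them: ρ, the correlation of log preoperative value with log peak (0.2–0.7); k, the SD of log baseline divided by the SD of log peak (0.5–1); and a treatment effect of 0.33 SD of log peak.

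**Formulas, in units of the log-peak variance.**
- Change score: V = 1 + k² − 2ρk
- ANCOVA: V = 1 − ρ²
- Excess variance of the change score = (k − ρ)²/(1 − ρ²), which is never negative
- Equivalent ANCOVA sample = 300/(1 + excess); CI width ratio = √(1 + excess)
- Power = Φ(0.33/√(2V/150) − 1.96)

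Example, k = 1 and ρ = 0.2: the change score has V = 1 + 1 − 0.4 = 1.60 and ANCOVA has V = 0.96. The excess is 0.64/0.96 = 66.7%, the CI is √1.667 = 1.29 times as wide, and 300/1.667 = 180.

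**Excess variance of a change score over ANCOVA**

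| k | ρ=0.2 | 0.3 | 0.4 | 0.5 | 0.6 | 0.7 | Equivalent ANCOVA N |
|---|---|---|---|---|---|---|---|
| 1 | 67% | 54% | 43% | 33% | 25% | 18% | 180–255 |
| 0.75 | 32% | 22% | 15% | 8% | 4% | <1% | 228–299 |
| 0.5 | 9% | 4% | 1% | 0% | 2% | 8% | 274–300 |

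**Power at the assumed effect, ρ = 0.2/0.4/0.6**

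| Method | k=1 | k=0.75 | k=0.5 |
|---|---|---|---|
| t-test on log change | 62/74/89% | 72/83/94% | 80/87/94% |
| Log ANCOVA | 83/88/95% | 83/88/95% | 83/88/95% |

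The peak with no adjustment has about 81% throughout. A change score beats ignoring the baseline only when ρ > k/2. A simulation with normal data at k = 1 (3,000 runs) agrees: 62/73/89% for log change and 83/86/94% for log ANCOVA. Under the null (ρ = 0.3, k = 1), every method rejected in 4.7–5.7% of runs.

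**Heavy tails.** Simulated power with a bivariate t distribution, 3 df, on the log scale, scaled to the same variance, ρ = 0.2/0.4/0.6:

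| Method | k=1 | k=0.5 |
|---|---|---|
| Log ANCOVA | 86/89/95% | 85/90/95% |
| Wilcoxon on log change | 87/94/99% | 96/99/100% |
| ANCOVA on ranks | 98/98/>99% | 98/99/100% |

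Here Wilcoxon on log change, which section 6.5 permits, matches or beats log ANCOVA.

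**Strata.** If site and eGFR explain 2/5/10% of the remaining variance (assumed), ignoring them inflates variance by 1/(1 − R²) − 1 = 2/5/11%. In simulation, adjusting for them gained about 1–2 points of power (82/82/83% unadjusted, 83/83/85% adjusted).

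**Which samples form the peak.** Section 5.4 isolates mononuclear cells only preoperatively and at the end of CPB, yet uses them to describe the monocyte phenotype postoperatively. The synopsis likewise lists monocyte phenotype among markers measured before and after surgery. In this plan's usage the end-of-CPB sample therefore counts as postoperative, and the peak is most naturally the highest of the four later samples.

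**The case against.** The strongest reply is that the sentence is workable. Either test can validly be run on a change score or a residual, each holds its error rate, and a residual on the same scale gives up nothing against ANCOVA. That stands: the defect is under-specification. It also stands that the size of any loss rests on the change-score reading and on two assumed quantities, and that preferring log ANCOVA because it yields a ratio with a confidence interval is partly a matter of taste. The GEE could take the baseline as a covariate, but the plan does not say that it will.

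Three stronger readings are tempting, and the documents do not support them.
- A reader might infer that the peak window is open, so that catalytic iron could lose its peak: section 1.2.2 reports that "Catalytic iron levels peaked at the end of CPB", while the troponin peak is tied to the 99th "percentile URL, assessed on POD1 and 2". That restriction belongs to the binary myocardial-injury endpoint alone. Nothing extends it to other markers, and section 5.4 points the other way.
- A reader might infer inflated type I error from the choice of reading. Choosing the smallest p-value among many readings would inflate it, but nothing in the plan proposes that, and each single test holds about 5%.
- A reader might take 67% as the expected loss. It is the top corner of the grid (k = 1, ρ = 0.2).

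**Conclusion.** The point holds as a minor one. The adjustment is undefined, the named tests cannot carry a covariate, the choice of test follows the data without a rule, and the strata are left out. On a change-score reading, the excess variance over ANCOVA is 0–67% across the assumed grid. Confidence intervals are 8–29% wider at k = 1, 0–15% at k = 0.75 and 0–5% at k = 0.5. The gain from ANCOVA is large only when k is near 1 and ρ is low. On a residual reading it is nil, and with heavy tails log ANCOVA can do worse than a rank method that the plan allows. Omitting the strata costs little. The case for acting therefore rests mainly on fixing one reproducible analysis in advance. The effect is confined to secondary and exploratory markers; the primary χ² test and the sample size are untouched.

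**What to change.** In section 6.5, for NGAL, KIM-1 and the iron and oxidative stress markers:
- Make the main peak analysis an ANCOVA of log peak on treatment, log preoperative value, site and eGFR stratum (<60 vs ≥60), reported as a ratio of geometric means with a 95% CI.
- Replace the distribution-driven choice of test with one fixed rank-based sensitivity analysis, for example ANCOVA on the ranks of the peak and the preoperative value with the same strata.
- State that the GEE includes the preoperative value as a covariate, if it is not already meant to. Keep the global-rank analysis for anuria.
- As a clarification only, confirm that the peak is the highest of the end-of-CPB, ICU-arrival, POD1 and POD2 values.

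The cost is SAP wording, with no new samples or patients. The downside is a log-linear assumption and the possible loss of power with heavy tails shown above, including against Wilcoxon on log change. The fixed rank-based analysis is there to cover that case.
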